3.8 SAFETY DATA

3.8.1 ADVERSE EVENTS (AE)

An Adverse Event (AE) is any untoward medical occurrence in a participant taking part in a research study, including occurrences which do not necessarily have a causal relationship with the research. This includes any psychological distress incurred by the participants, which could be caused by threatening phone messages or aspects of their probation.

Following the baseline interview, researchers will record any adverse events disclosed by participants and/or their (ex)-partners.

$3.8.2\,$ ADVERSE EVENTS EXPERIENCED BY PARTNERS/ EX-PARTNERS CONSENTED INTO THE TRIAL CAUSED BY THE PROBATIONER

When an event occurs that has been initiated by the probationer that leads to harm to the consenting partner/ex-partner it will be recorded under the AE log of the probationer as occuring on the partner/ex-partner. If any of the adverse events caused by the probationer fall under notifibale probation incidents and offences this will be recorded. This includes death, attempted murder, murder, manslaughter, rape, grevious bodily harm and terrorism-related offence. To report non-medical notifiable incidences and offences, see section 3.9 Non-medical Criminal Justice Occurences.

3.8.3 ADVERSE EVENTS EXPERIENCED BY INDIVIDUALS NOT CONSENTED INTO THE TRIAL CAUSED BY THE PROBATIONER

When an event that has occured that has been initiated by the probationer that leads to harm experienced to individuals outside of the trial it will be recorded under the AE log of the probationer as occuring on another person. This information can only be learned through the probation officer. No identifying characteristics of the person harmed will be collected. This will include children of the participants as well as others (e.g., partners not consented and other members of the public and emergency services). If any of the adverse events caused by the probationer fall under notifibale probation incidents and offences, this will be recorded. This includes death, attempted murder, murder, manslaughter, rape, grevious bodily harm and terrorism-related offence. To report non-medical notifiable incidences and offences, see section 3.9 Non-medical Criminal Justice Occurances.

3.8.4 SERIOUS ADVERSE EVENTS (SAE)

A Serious Adverse Event (SAE) is any untoward medical occurrence that: results in death; is life-threatening; requires inpatient hospitalisation or prolongation of existing hospitalisation; results in persistent or significant disability/incapacity or consists of a congenital anomaly or birth defect. Other 'important

events' may also be considered serious if they jeopardise the participant or require an intervention to prevent one of the above consequences.

3.8.5 SERIOUS ADVERSE EVENTS EXPERIENCED BY INDIVIDUALS NOT CONSENTED INTO THE TRIAL CAUSED BY THE PROBATIONER

All SAEs will be followed up by the researcher, the PP/JSW or ISS worker. If men are rearrested for IPV during the trial, a case management meeting will be held to determine whether the participant can remain in the trial and to provide additional safeguarding to their (ex)-partner if required. As listed above, when an event occurs that has been initiated by the probationer that leads to harm experienced to individuals outside of the trial it will be recorded under the AE log of the probationer as occuring on another person. This information can only be learned through the probation officer. No identifying characteristics of the person harmed will be collected. An adverse event will be upgraded to a serious adverse event if the harm caused falls into the category of an SAE i.e. results in death; is life-threatening; requires inpatient hospitalisation or prolongation of existing hospitalisation; results in persistent or significant disability/incapacity or consists of a congenital anomaly or birth defect.

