1.1 BACKGROUND AND RATIONALE

Around 1 in 3 women experience intimate partner violence (IPV), defined as any behaviour by an (ex)intimate partner causing physical, sexual or psychological harm, including aggression, sexual coercion, psychological abuse, financial abuse and controlling behaviours¹ resulting in poor mental, physical and sexual health.^{2,3} Having a male partner who misuses alcohol and/or drugs (substances) increases the risk of experiencing IPV and of domestic homicide. 4,5 Delivering effective targeted behaviour change interventions to male IPV perpetrators who misuse substances will reduce the harm to their female (ex)-partners. However, the Domestic Abuse Commissioner for England and Wales has recently highlighted the lack of access to perpetrator programmes, 6 with less than 1% of perpetrators receiving specialist behaviour change interventions.7

While no single factor explains why some men are more likely to perpetrate IPV, substance misuse, especially dependence, is a consistent risk factor.^{8,9} Rates of IPV perpetration for men who misuse substances are up to 4 times higher than for men who do not. 10,111 We found that around 6 in 10 men in substance misuse treatment in England had ever perpetrated any IPV and 4 in 10 had done so in the past year, with 1 in 10 reporting perpetrating severe IPV in the past year. 11,12 Substance dependent men are 7 times more likely to be arrested for IPV, ¹³ and to abuse multiple victims. ¹⁴ Despite this elevated prevalence, men in substance misuse treatment are rarely referred to perpetrator programmes. 15-17 Few men in our study had ever received support for their abusive behaviour. ¹⁸ Moreover, men with substance misuse problems make up at least 50% of men in community and court mandated perpetrator interventions. 19,20 They are among the most high-risk and highly resistant groups of IPV offenders. 21,22 Recidivism for court-mandated IPV offenders who misuse substances is around 20-30%. 23 They are also more likely to drop out of courtmandated perpetrator programmes, ^{20,22} suggesting that integrating substance misuse treatment to IPV interventions can prevent reoffending in this group.²¹

Gap in the delivery of perpetrator interventions in probation that are responsive to substance misuse and the additional risks it presents

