3.7 EFFICACY DATA

Participant self-report measures will be administered by the researcher in the absence of the PP/ JSW (men only) and (ex)-partners. Short, medium, and longer-term outcomes for men and their (ex)-partners will be assessed by research interview at 4 and 12-months and via linkage with health and criminal justice records at 24 months post-baseline. Researchers will collect outcome data, conducting interviews by phone, Microsoft Teams or in-person at PDU/ JSWT (men) or ISS, library or children's centre (women) 4 and 12-months with both men and their (ex)-partners. Outcomes will be analysed using the modified intention to treat (ITT)

population at 4 and 12 months. Even if the male participant has dropped out of the intervention, they will be followed-up, unless they have asked to be withdrawn from the study. All measures have been successfully used in our previous studies. ^{47,48} In our previous trial of ADVANCE, ⁴⁷ the suitability and acceptability of outcome measures were assessed with both male and female participants using the researchers' perceptions of participants' understanding (language and meaning of questions) and acceptability (participant refused to answer, got annoyed/frustrated or asked to end the interview) for each outcome measure using a predetermined rating scale scored from 1 (lowest rating) to 3 (highest rating). Completeness of outcome data was determined for each measure for both male and female participants. Therefore, the measures selected for primary and secondary outcomes for the proposed study have been demonstrated to be understandable and acceptable to participants. In addition, the time required to complete the assessments in person and by phone are also acceptable to participants. Record linkage will be performed at 24 months.

The table below outlines the instruments administered to male perpetrators and their female current or ex-partners to be included in the study.

Outcome	Male per	petrators	Femal	e survivors
	Baseline	4 & 12- months post	Baseline	4 & 12- months post
		baseline interview		male baseline interview

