3.8.8 WITHDRAWAL

Withdrawal will be categorised as 1) Participant withdrawal; 2) PDU/JSWT or researcher withdrawal of participant. If the male or female participant withdraws or is withdrawn from the trial, their (ex)-partner will still be followed-up.

(1) Participant wishes to withdraw from the trial and not provide outcome data

Participants have the right to withdraw from the trial at any time for any reason. Should a participant decide to withdraw from the study, all efforts will be made to report the reason for withdrawal as accurately as possible. If participants do choose to withdraw from the study or if they are no longer able to give their consent to continue in the study, the research team will delete their contact details but will need to use the anonymous data collected up to the point of withdrawal. This is explained to participants in the PIS If men withdraw from the study and had been given a tablet by the research team, they will be asked to return this by courier (organised and paid for by the research team) or to the substance use treatment service.

Participants have the right to withdraw from future record linkage with health or social care services or the criminal justice system. Current or (ex)-partners will not be informed of withdrawal.

(2) Participant is withdrawn from the trial by PDU/JSWT or research team

PDU/JSWT or the research team also have the right to withdraw participants from study in the event of adverse incidents or severe adverse events (SAEs) or other reasons which would be discussed on a case-bycase basis with the ADVANCE-D Clinical lead. Unnecessary withdrawal of participants should be avoided.

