5.4 BLINDING STATUS OF RESEARCHERS

Researchers (outcome assessors) will be blind to group allocation when baseline interviews with male participants and their current or ex female partners are conducted. After the men are baselined from each PDU/ JSWT and their (ex)-partners have been completed their baseline assessment or declined to take part in the research or were not contactable, they will be informed of allocation. Probation practitioners and principal investigators/other staff at PDU/ JSWT will be blind during eligibility and consent.

Individual blinding status	Blinded	Unblinded
Chief Investigators	X	
Principal Investigators and all other PDU/JSWT staff at site (blinded until post baseline)		X
Co-applicants ^α	X	
Trial Manager		X
Facilitators		X
Senior Trial Statistician	X	
Trial Statistician ^a	X	
Senior Health Economist	X	
Health Economist (blinded until after data collection)	X	
Trial Participants		X
Outcome Assessors (blinded during baseline interview)		X
Partner Support Workers		X
Trial Steering Committee (TSC)	X	
Data Monitoring Committee (DMC)		X

Table 6. Blinding Status

^aThe blinding status of the research team is detailed in Table 6 above. Note the Trial Statistician will become partially blinded at the point of reporting to the Data Monitoring Committee outcome and safety data partitioned in groups labelled A and B. The time of when this planned change in blinding status of the Trial Statistician is will be reported. The Clinical Lead (co-applicant [name]) will be unblinded.

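### Staff, most of them unblinded, may remove men from the trial after IPV re-arrest or adverse incidents, and later collection of the primary outcome from these men is not secured

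*Protocol*

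**What the plan says.** Two provisions let staff take a man out of the trial itself, not just out of the programme.

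- Protocol section 3.8.5: "If men are rearrested for IPV during the trial, a case management meeting will be held to determine whether the participant can remain". The reference is to the trial.
- Protocol section 3.8.8, category 2: "PDU/JSWT or the research team also have the right to withdraw participants from study in the event of adverse incidents or severe adverse events". Other reasons are also allowed, discussed case by case with the clinical lead. The only limit is general: "Unnecessary withdrawal of participants should be avoided".

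On follow-up after removal, section 3.8.8 says: "If the male or female participant withdraws or is withdrawn from the trial, their (ex)-partner will still be followed-up". It does not say what happens to the man's own interviews when staff withdraw him. Section 3.7 says of men who leave the intervention: "Even if the male participant has dropped out of the intervention, they will be followed-up", with one exception, the man's own request to be withdrawn. The adherence text in section 4.1.1 promises efforts to obtain follow-up data after withdrawal from the programme, with the man's permission.

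Table 6 in section 5.4 lists as unblinded "Principal Investigators and all other PDU/JSWT staff at site (blinded until post baseline"), and also facilitators, partner support workers and, after the baseline interview, outcome assessors. Its footnote says the clinical lead is unblinded.

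The primary outcome is the self-reported ABI total at 12 months, covering the previous 4 months (sections 3.7.1 and 10.1). The ITT population in section 10.4.1 consists of participants followed up at 4 or 12 months.

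**The concern.** Re-arrest for IPV is closely related to what the primary outcome measures. If it leads to a man leaving the trial, and leaving the trial means no further interviews, the primary outcome goes missing for a reason connected with its own value. A man removed before month 4 has no follow-up and falls outside the ITT population. A man removed later contributes at most his 4-month score, and the mixed model treats his 12-month score as missing at random.

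The loss may also differ between arms. The decisions are made largely by people who know the allocation. Weekly coaching, support-service contact with partners and scheduled case management meetings belong to ADVANCE-D (sections 3.4.15 and 4.1.1), while partners of control men get usual support, if any (section 3.3). Incidents may therefore come to notice, and be discussed, more often in one arm. What is at stake is the validity of the 12-month comparison. An analysis plan cannot restore interviews that were never held.

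**Working it through.** **Reading the passages together**

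| Situation | Is the man's own follow-up secured? |
|---|---|
| Stops the programme (sections 3.7, 4.1.1) | Yes, unless he asks to leave the study; section 4.1.1 adds that his permission is needed |
| Withdraws himself from the trial (3.8.8, category 1) | No; data up to withdrawal are kept |
| Withdrawn by site or research staff (3.8.8, category 2) | Not stated |
| Not allowed to remain after re-arrest (3.8.5) | Not stated |

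The last two rows are the gap.

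**The plan's own figures (section 10.3)**

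For 0.4 SD, 90% power and two-sided 5%, the t-based size is 133 per arm, 266 in total, as stated. The design effect is 1 + (13.5 − 1) × 0.03 = 1.375, and 266 × 1.375 = 366, against 358 stated (2.2% higher). Allowing for 18% dropout, 358/0.82 = 437 and 366/0.82 = 447, against 450 stated. No stated figure is in dispute. The standard error of the contrast at 358 analysed is √(1.375 × 4/358) = 0.124 SD.

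**Illustration of size**

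The protocol gives neither the share of re-arrested men who would be withdrawn nor the correlation with the ABI. Assumptions:

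- p = 25% re-arrested in control. This is the middle of the range in section 1.1, "Recidivism for court-mandated IPV offenders who misuse substances is around 20-30" per cent. That range has no time window and is not defined as re-arrest.
- ρ = 0.3, 0.5 or 0.7 between a normal re-arrest liability and the standardised 12-month ABI.
- w = share of re-arrested men withdrawn and not interviewed.
- No credit for baseline or 4-month adjustment.

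With no true effect, the mean of the men retained in an arm shifts by −ρ × w × φ(z)/(1 − w × p). Here z = 0.674 and φ(z) = 0.318. The multipliers of ρ are:

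- w = 100%: 0.318/0.75 = 0.424
- w = 50%: 0.159/0.875 = 0.182
- w = 20%: 0.0636/0.95 = 0.067
- w = 10%: 0.0318/0.975 = 0.033

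False benefit under no effect, with the larger share withdrawn in the intervention arm:

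| Withdrawn, intervention vs control | ρ = 0.3 | ρ = 0.5 | ρ = 0.7 |
|---|---|---|---|
| 20% vs 10% | 0.010 | 0.017 | 0.024 |
| 100% vs 50% | 0.07 | 0.12 | 0.17 |

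At ρ = 0.5 the two-sided type I error is about 5.2% in the first row (0.017/0.124 = 0.14 SE) and about 16% in the second (0.121/0.124 = 0.98 SE).

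With a true effect of 0.4 SD, the intervention arm's re-arrest threshold moves by 0.4ρ. Results at ρ = 0.3/0.5/0.7:

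- All re-arrested men withdrawn in both arms: 0.38/0.36/0.32 SD observed.
- Half withdrawn in intervention, all in control: 0.32/0.26/0.20 SD observed.

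The bias can therefore go either way. The 100% versus 50% case is an upper scenario: it loses on average 25% × (100% + 50%)/2 = 18.75% of men from this cause alone, more than the whole 18% dropout allowance.

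**The case against.** The strongest reply is that the protocol never orders any loss of outcome data.

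- **Follow-up may already be protected.** The phrase about not providing outcome data is attached only to participant-initiated withdrawal. Section 3.7 allows one exception to follow-up, the man's own request. The sentence about the (ex)-partner can be read as saying only that one member of a couple leaving does not remove the other. This stands as a fair reading, but it is not the only one, and site staff should not have to choose.
- **Nothing is deleted.** A reader might infer that the worst ABI values are erased. The documents do not support this: section 3.8.8 keeps data up to withdrawal (stated under participant-initiated withdrawal), and nothing removes a recorded value. The risk is that later scores are not collected.
- **The worst scores are not shown to be the ones lost.** The 12-month ABI covers only the previous 4 months. A man re-arrested earlier may be in custody or separated in that window, so the correlation, even its sign, is not known from the documents.
- **Detection may not differ for re-arrest.** Men in both arms have a supervising officer, so arrests may be known equally. The argument for differential detection applies better to other incidents.
- **Not everyone is unblinded.** Chief investigators and co-applicants other than the clinical lead are listed as blinded.
- **Section 10 is not contradicted.** A reader might see a conflict because return to prison is named as an intercurrent event. That list is open and the full estimand is left to the SAP.
- **Mitigation is planned.** Pattern-mixture analysis (section 10.8), sensitivity analyses for intercurrent events (10.4.1, 10.11) and 24-month linkage to IPV arrests and convictions (3.7.9) all help. None recovers a 12-month ABI score that was not collected.

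**Conclusion.** The concern holds as a gap in wording with a real route to bias. Sections 3.8.5 and 3.8.8 permit removal from the trial for events closely related to the primary outcome, by staff who are mostly unblinded, with no criteria beyond avoiding unnecessary withdrawal. They do not secure later ABI collection, and they sit uneasily with sections 3.7 and 4.1.1. The missingness may be outcome-related and may differ by arm.

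The direction and size are unknown. With 25% re-arrest and a correlation of 0.5, both assumed, the bias runs from about 0.02 SD for modest unequal withdrawal to about 0.12 SD in the upper scenario, against a 0.4 SD target. The documents do not support a claim that the type I error will be 16%; that figure belongs to the upper scenario only. The case for acting now does not depend on that figure: missed interviews cannot be recovered by any analysis, and the change is small.

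**What to change.** Reconcile sections 3.7, 3.8.5, 3.8.8 and 10.4.1 on these lines:

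1. A staff decision to end the programme or active participation is separate from ending outcome collection.
2. Unless the man himself withdraws consent, he stays in the analysis population and the 24-month linkage, and is approached for the 4- and 12-month ABI where the safeguarding assessment allows.
3. Every staff-initiated withdrawal is logged by arm, reason and date, and treated as an intercurrent event.

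The wording should concern outcome collection only. Section 3.2.4 recognises that the clinical team may end a man's participation because of increased risk to either party, and the change should leave that power intact. No position is taken here on when the programme should stop or on any safeguarding decision.

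The cost is a protocol amendment and a staff briefing. Some interviews will be harder to arrange, for example in custody. The sample size does not change.

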3.8.6 RECORDING AND REPORTING

All deaths will be reported to the sponsor within 24 hours of receiving the notification by the CI. All SAEs will be recorded on the relevant form of the CRF and the Trial Manager will report this to the CI and DMC chair within 24 hours of receiving the report. The CI and DMC chair will consider whether the SAE is: not related to participation in the trial; possibly related to participation; or definitely related to participation within 24 hours of receiving the report. Judgement will be made on whether to report the possibly related cases on to the Sponsor and REC chair, but all cases of definitely related will be reported onwards.

Where safeguarding or distress protocols are followed, or where interviewers' safety is threatened, an incident report form will be completed by the researcher. The CI will be notified of any incidents as soon as possible. All incidents and resulting actions will be recorded on an incident report and emailed to the trial manager who will store them on SharePoint. Only ID numbers will be included on the incident form. A cumulative review of all safety information by the DMC will be made on a six-monthly basis.

Judgement will be made on whether to report the possibly related cases on to the Sponsor and ethics committee chair, but all cases of definitely related SAE will be reported onwards. All SAEs will be followed up where appropriate by the researcher, the intervention facilitator, PP/JSW or the women's worker. If it is felt that a child or adult are at significant risk, then the standard safeguarding procedure for the service will be followed.

Only unexpected and related serious adverse events (SAE) resulting from trial participation will be reported to the REC and the sponsor within 24 hours of receiving the report.

3.8.7 CONCOMITANT INTERVENTIONS/ TREATMENT

During each research interview, participants will be asked about their use of other interventions/ treatment. All concomitant interventions/ treatment will be recorded in an ongoing concomitant interventions/treatment log.

3.8.8 WITHDRAWAL

Withdrawal will be categorised as 1) Participant withdrawal; 2) PDU/JSWT or researcher withdrawal of participant. If the male or female participant withdraws or is withdrawn from the trial, their (ex)-partner will still be followed-up.

(1) Participant wishes to withdraw from the trial and not provide outcome data

Participants have the right to withdraw from the trial at any time for any reason. Should a participant decide to withdraw from the study, all efforts will be made to report the reason for withdrawal as accurately as possible. If participants do choose to withdraw from the study or if they are no longer able to give their consent to continue in the study, the research team will delete their contact details but will need to use the anonymous data collected up to the point of withdrawal. This is explained to participants in the PIS If men withdraw from the study and had been given a tablet by the research team, they will be asked to return this by courier (organised and paid for by the research team) or to the substance use treatment service.

Participants have the right to withdraw from future record linkage with health or social care services or the criminal justice system. Current or (ex)-partners will not be informed of withdrawal.

(2) Participant is withdrawn from the trial by PDU/JSWT or research team

PDU/JSWT or the research team also have the right to withdraw participants from study in the event of adverse incidents or severe adverse events (SAEs) or other reasons which would be discussed on a case-bycase basis with the ADVANCE-D Clinical lead. Unnecessary withdrawal of participants should be avoided.

